### **5.5.2.1 Twelve- and Eighteen-Month Failure Rates**

The same approach employed for the primary analysis will be used for the analyses of the twelve-month failure rate (until Day 365) and the eighteen-month failure rate (until Day 547 or scheduled EoT).

The following statistical outputs will be presented:

Table 15.2.2.1 Analysis of Treatment Failure Rate within 12 Months after Randomisation – Full Analysis Set

Table 15.2.2.2 Analysis of Treatment Failure Rate within 12 Months after Randomisation – Per-Protocol Set

Table 15.2.3.1 Analysis of Treatment Failure Rate within 18 Months after Randomisation – Full Analysis Set

Table 15.2.3.2 Analysis of Treatment Failure Rate within 18 Months after Randomisation – Per-Protocol Set

Number and percentage of failures (overall, US, death, early withdrawal, missing) and non-failures 12 or 18 months after randomisation will be tabulated, including degrees of freedom (DF), value and p-value for chi-square test, p-value for fisher's exact test, RD of failing between ESL and Placebo with corresponding 95% continuity-corrected Newcombe CI as well as ESL vs Placebo OR with 95% score confidence interval.

### **5.5.2.2 Number of Acute Symptomatic Seizures**

The number of patients that experience at least one AS will be analysed.

The following statistical outputs will be created:

Table 15.2.4.1 Summary of Acute Symptomatic Seizures – Full Analysis Set

Table 15.2.4.2 Summary of Acute Symptomatic Seizures – Per-Protocol Set

The number of ASs will be summarised by means of descriptive statistics for patients with at least one AS (FAS and PPS) by treatment group and in total. The number and percentage of patients without and with AS(s) will be incorporated into the table.

### **5.5.2.3 Time to First Unprovoked Seizure after Randomisation**

For the following analyses, patients will be censored at their last day in the trial.

The time to first US after randomisation will be analysed and presented by means of the Kaplan-Meier estimate (including censored data e.g. withdrawals) after 6, 12 and 18 months for the failure time and corresponding simultaneous CI, a log-rank test (p-value) as well as estimates for 25% percentile, median, and 75% percentile failure time and corresponding CI. The time to first US will be analysed from the day of randomisation.

For this purpose, the following SAS code will be used:

```
ODS OUTPUT Quartiles=quartiles;
ODS OUTPUT ProductLimitEstimates=limit;
ODS OUTPUT HomTests= tests;
PROC LIFETEST DATA=<dataset> METHOD=KM CONFBIAS=EP TIMELIST= 182 365 547;
  TIME <Time to first US>*<Status> (0);
  STRATA <Treatment group> /TEST=LOGRANK;
RUN;
```

The Kaplan-Meier product limit estimate and simultaneous equal precision 95% confidence bands will be graphed.

In case of deaths before the first US, the competing risk of deaths and US will be evaluated exploratively using cause-specific cumulative incidence function and Gray's test for homogeneity in addition.

The following SAS code will be used:

Note: the status will be 0 for censored observations, 1 if US occurred and 2 if the patient died before experiencing an US.

```
ODS OUTPUT GrayTest= graytest;
```

```
PROC LIFETEST DATA=<dataset>;
  TIME <Time to first US or death>*<Status> (0) /eventcode=1;
  STRATA <Treatment group> / order=internal;
RUN;
```

The following statistical outputs will be presented:

Table 15.2.5.1.1 Time to First Unprovoked Seizure after Randomisation– Full Analysis Set

Table 15.2.5.1.2 Time to First Unprovoked Seizure after Randomisation – Per-Protocol Set

The time to first US after randomisation will be presented by estimates for 25% percentile, median, and 75% percentile failure time and corresponding CI; means of the Kaplan-Meier estimate after 6, 12 and 18 months for the failure time and corresponding simultaneous CI (equal precision bands) and the p-value of a log-rank test

Figure 15.2.1.2.1 Time to First Unprovoked Seizure after Randomisation – Full Analysis Set

Figure 15.2.1.2.2 Time to First Unprovoked Seizure after Randomisation – Per-Protocol Set

The Kaplan Meier Product Limit Estimate and simultaneous equal precision 95% confidence bands will be presented for the treatment groups.

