### **5.5.2.8 Overall Survival**

Overall survival (time to death relative to the date of randomisation) will be analysed and presented by means of the Kaplan-Meier estimates (including censored data e.g. withdrawals) after 6 months (Day 182), 12 months (Day 365) and 18 months (Day 547) for the survival rates including pointwise CI, log-rank test as well as estimates for 25% percentile, median, and 75% percentile survival time and corresponding CI.

For this purpose, the following SAS code will be used:

```
ODS OUTPUT Quartiles=quartiles;
ODS OUTPUT ProductLimitEstimates=limit;
ODS OUTPUT HomTests= tests;
PROC LIFETEST DATA=<dataset> METHOD=KM TIMELIST= 182 365 547;
  TIME <Time to death>*<Status> (0);
  STRATA <Treatment group> /TEST=LOGRANK;
RUN;
```

Kaplan-Meier plot for overall survival will be presented.

The following statistical outputs will be presented:

Table 15.2.9.1 Overall Survival – Full Analysis Set

Table 15.2.9.2 Overall Survival – Per Protocol Set

Number and percentage of patients who died and patients censored will be tabulated. The time to death in days will be presented by estimates for 25% percentile, median, and 75% percentile and corresponding CI; means of the Kaplan-Meier estimate after 6, 12 and 18 months for the time to death and corresponding pointwise CI and the p-value of a log-rank test will be presented.

Figure 15.2.5.1 Overall Survival – Full Analysis Set

Figure 15.2.5.2 Overall Survival – Per Protocol Set

The Kaplan-Meier Product Limit Estimate and simultaneous equal precision 95%-Confidence bounds will be presented.

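### Kaplan-Meier seizure estimates at three pre-set days carry whole-curve limits, and the time-to-event analyses compare the arms only by p-values

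*SAP*

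**What the plan says.** SAP 5.5.2.3 censors patients at their last day in the trial and estimates time to first US by Kaplan-Meier. The text asks for estimates at 6, 12 and 18 months "for the failure time and corresponding simultaneous CI, a log-rank test (p-value". The code fixes the reading times: "METHOD=KM CONFBIAS=EP TIMELIST= 182 365 547" (the first option name is shown as printed; nothing here depends on it). The description of Tables 15.2.5.1.1 and 15.2.5.1.2 names the type of limit: "corresponding simultaneous CI (equal precision bands) and the p-value of a log-rank test". The same bands are drawn in Figures 15.2.1.2.1 and 15.2.1.2.2. If deaths occur before a first US, the section adds an exploratory "cause-specific cumulative incidence function and Gray's test for homogeneity in addition".

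SAP 5.5.2.8 reports overall survival at the same three days with the other type of interval: "18 months (Day 547) for the survival rates including pointwise CI, log-rank test". Its figures use the whole-curve type: "The Kaplan-Meier Product Limit Estimate and simultaneous equal precision 95%-Confidence bounds will be presented".

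Neither section plans a hazard ratio, a difference between the arms, or any other between-arm estimate with an interval.

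**The concern.** There are two linked issues.

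First, an equal-precision band is calibrated so that the whole curve lies inside it with 95% confidence. A table that reports three pre-set days does not need that protection. A reader who takes the limits at Day 182 as an ordinary 95% interval will think the trial less precise than it is. The SAP gives no reason for treating seizures differently from survival.

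Second, the time-to-event analyses are where the follow-up of patients who leave is used up to the day they leave. If these analyses yield only p-values, they cannot show how large an effect on seizures or deaths the data allow or exclude. This matters because recruitment stopped short of plan (SAP 2.6 and section 8), so non-significant p-values may well need interpreting.

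**Working it through.** **1. Inputs.** The documents state no interval width, so there is no such figure to reproduce. The planned size of 100 per arm (29.7% against 12.6%, continuity-corrected) does reproduce, with power 80.1%, and serves as the upper end for n. The realised number is not given, so 30 to 100 per arm is assumed. The cumulative seizure incidence at the end of follow-up is also assumed, at 8 to 40%. The values 8% and 26% are borrowed from the planned 6-month failure rates, which include deaths and are not 18-month seizure risks.

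**2. Band multiplier.** The asymptotic equal-precision multiplier c solves

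4φ(c)/c + φ(c)(c − 1/c) ln[aU(1 − aL) / (aL(1 − aU))] = 0.05,

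with a = nσ²/(1 + nσ²). Without censoring nσ² = F/(1 − F), so a equals the cumulative incidence F. Hence aL ≈ 1/n (first event) and aU = F at the last event.

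Example, n = 100 and F = 0.26: ln[(0.26 × 0.99)/(0.01 × 0.74)] = 3.549. At c = 2.984, φ(c) = 0.00465. The two terms are 0.0062 and 0.0437, which sum to 0.05 within rounding. The ratio is 2.984/1.96 = 1.52.

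| n per arm | F = 8% | F = 26% | F = 40% |
|---|---|---|---|
| 30 | 2.59 (1.32) | 2.85 (1.45) | 2.92 (1.49) |
| 50 | 2.71 (1.38) | 2.91 (1.49) | 2.98 (1.52) |
| 100 | 2.82 (1.44) | 2.98 (1.52) | 3.04 (1.55) |

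The ratio to 1.96 is in brackets. The corner at n = 30 and 8% rests on 30 × 0.08 = 2.4 expected events, so the asymptotic value is weak there.

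**3. Alternative for three days.** If joint coverage of the three days were wanted, Bonferroni needs z at 1 − 0.05/6, which is 2.39 (1.22 times 1.96). That is below every band value in the table.

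**4. Width in percentage points.** At F = 26% without censoring, SE = √(0.26 × 0.74/n):

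- n = 60: SE = 5.66 points; ±11.1 pointwise, ±16.6 with the band (c = 2.93).
- n = 100: SE = 4.39 points; ±8.6 pointwise, ±13.1 with the band.

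**5. Log-log scale with censoring.** In simulation with an assumed 20% drop-out over 18 months, 30 to 100 per arm and 15 to 40% incidence, the ratio of full widths was about 1.6 to 1.7 at 6 months, 1.5 to 1.6 at 12 months and 1.46 to 1.54 at 18 months. For n = 50 and 26% at 18 months, the full width at 18 months was 0.39 with the band and 0.26 pointwise.

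**6. Between-arm results, side by side.**

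| Analysis | Patients who leave or die | Arms compared by |
|---|---|---|
| Failure rate at 6, 12, 18 months (SAP 5.5.1, 5.5.2.1) | failures | risk difference and odds ratio with 95% CI, tests |
| Seizures only at 6, 12, 18 months (SAP 5.5.1.1) | non-failures | risk difference and odds ratio with 95% CI, tests |
| Kaplan-Meier, first US (SAP 5.5.2.3) | censored at last day | log-rank p-value |
| Cumulative incidence, US (SAP 5.5.2.3) | leavers censored, death competing | Gray's test p-value |
| Overall survival (SAP 5.5.2.8) | leavers censored | log-rank p-value |

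The 6-month multiple-imputation analysis in SAP 5.5.1.1 also gives a risk difference and odds ratio. It concerns US or death combined and imputes outcomes for withdrawals.

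**7. What a survival p-value leaves unsaid.** With d deaths in total, split about equally, the 95% factor around a hazard ratio is exp(1.96 × 2/√d). The number of deaths is not given. Assuming d = 10, 20 or 40, the factor is 3.4, 2.4 or 1.9.

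**The case against.** A reader might infer that no between-arm estimate for seizures over time is planned at all. The documents contradict that: Tables 15.2.1.5.1 to 15.2.1.5.6 give risk differences and odds ratios with 95% intervals for seizures alone at 6, 12 and 18 months. The gap is confined to the time-to-event analyses. Within that limit it stands, because a patient lost in week 3 counts in those tables as free of seizures for 18 months.

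A reader might also infer that the equal-precision limits are wrong. They are not. The SAP calls them simultaneous and nowhere presents them as pointwise, and they match the bands in the seizure figures. The case against them is fitness for a table of three pre-set days.

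Nor is Kaplan-Meier the only planned seizure estimate that uses censored follow-up. The cumulative incidence function does so too, and the protocol synopsis announces it. It is exploratory, however, and no table or figure for it is listed in SAP 5.5.2.3, 10.1 or 10.3.

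For survival, the per-arm counts and pointwise intervals let a reader work out an approximate difference. That is true, but the plan should report it directly.

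Finally, one hazard ratio may be hard to interpret when about 30 days of treatment are followed for 18 months. That objection stands, and it is why the differences at fixed days should come first. These are also secondary analyses in a self-described pilot, which limits the weight of the point.

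**Conclusion.** The point holds as a cheap improvement, and it reveals no error in the primary analysis. Read at a single day, the tabulated seizure limits are about 1.3 to 1.55 times the pointwise width on the standard-error scale, and wider still at 6 months on the log-log scale in the simulation. These sizes rest on assumed numbers per arm, incidence and drop-out. The direction does not: every multiplier computed exceeds both 1.96 and the three-day Bonferroni value of 2.39. That the time-to-event analyses of first US and of overall survival compare the arms only by p-values follows from the SAP text and needs no assumption.

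**What to change.** - In Tables 15.2.5.1.1 and 15.2.5.1.2, report pointwise 95% intervals on the log-log scale at Days 182, 365 and 547. Keep the equal-precision bands in the figures.
- For first US, add the ESL minus placebo difference with a 95% interval at the three days, taken from the cumulative incidence function already planned, with death as the competing event. Show the per-arm cumulative incidences beside it so that the difference can be traced.
- In Tables 15.2.9.1 and 15.2.9.2, add the Kaplan-Meier survival difference, ESL minus placebo, with a 95% interval at the same days.
- A Cox hazard ratio with a 95% interval may be added as a supportive summary. For US it should be labelled cause-specific, and a note should say that proportional hazards is doubtful here.

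The cost is SAP wording, a few more table rows and a few program lines. No new data are needed and the primary analysis is unchanged.

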#### **5.5.2.4 Number of Unprovoked Seizure**

The total number in all patients and in patients with US(s) only will be summarised by means of descriptive statistics.

The following statistical output will be presented:

Table 15.2.5.4.1 Summary of Unprovoked Seizures– Full Analysis Set

Table 15.2.5.4.2 Summary of Unprovoked Seizures – Per-Protocol Set

Number and percentage of patients with and without US(s) will be presented. The total number of USs will be summarised by means of descriptive statistics for all patients and for patients that experienced US(s).

#### **5.5.2.5 Barthel Index**

BI data is collected at V1a, V3, V5, V7 and EOT or EDV and, if applicable, UNS.

The BI is a widely used score to measure the performance in activities of daily living of patients with stroke and other neuromuscular or musculoskeletal disorders in the following 10 categories:

1. Feeding (scored as 0, 5, 10)
2. Moving from a wheelchair to a bed and back again (scored as 0, 5, 10, 15)
3. Personal hygiene (scored as 0, 5)
4. Getting on and off the toilet (scored as 0, 5, 10)
5. Self-bathing (scored as 0, 5)
6. Walking on a level surface (scored as 0, 5, 10, 15)
7. Ascending and descending stairs (scored as 0, 5, 10)
8. Dressing (scored as 0, 5, 10)
9. Controlling bowels (scored as 0, 5, 10)
10. Controlling bladder (scored as 0, 5, 10)

Items are weighted according to the level of nursing care required and are rated in terms of whether individuals can perform activities independently, with some assistance, or are dependent (scored as 0, 5, 10 or 15). The total BI score (possible range 0 – 100) will be calculated as the sum of the individual scores from each item.

General ranges of BI describe patients' disability as follows:

80-100 – patient should be able to live independently

60-79 – minimally dependent

40-59 – partially dependent  
20-39 – very dependent  
<20 – total dependence.

The BI can be used to determine a baseline level of function and to monitor improvements in activities of daily living over time [4].

The BI total score at baseline and post-baseline visits of each patient will be calculated adding the individual scores from each item.

The BI total score and its change from baseline at each time of examination will be summarised by means of descriptive statistics. Differences between the treatment groups (ESL-Placebo) will be evaluated exploratively using multiple exact Wilcoxon-Mann-Whitney Test and exact Hodge-Lehmann CIs at each time of examination.

The following SAS Code will be used:

**Note: Data should be sorted by treatment group (first “ESL” then “Placebo”)**

```
proc npar1way hl correct=no alpha=.05 data=<dataset>;
  class <treatment_group>;
  var <change from baseline of BI_total_score at specific timepoint>;
  exact wilcoxon;
  exact hl;
  ods select WilcoxonScores WilcoxonTest HodgesLehmann;
run;
```

If this SAS code runs for more than 10 minutes, maxtime=50 will be used and the normal approximate result will be tabulated. A higher maxtime does not lead to a change of the result.

Cumulative incidence of USs will be illustrated using Kaplan-Meier curves by the BI Baseline categories (<=79, 80-100) and treatment group. Patients without an event or lost to follow-up will be censored at their last visit or termination date. Time to event will be calculated from time of randomisation to first US.

The following statistical outputs will be presented:

[Table 15.2.6.1.1 Summary of Barthel Index Total Score – Full Analysis Set](#)

[Table 15.2.6.1.2 Summary of Barthel Index Total Score – Per-Protocol Set](#)

The default summary statistics for the BI total score will be presented by visit slots by treatment group at Baseline, V3, V5, V7, EOT, EDV (if applicable) and Endpoint.

[Table 15.2.6.2.1 Analysis of Barthel Index Total Score Differences – Full Analysis Set](#)

[Table 15.2.6.2.2 Analysis of Barthel Index Total Score Differences – Per-Protocol Set](#)

The Hodges-Lehmann estimate of location shift and the corresponding 95% CIs including the Wilcoxon Mann Whitney test p-value will be presented by visit slots for V3, V5, V7 and Endpoint for ESL-Placebo.

[Figure 15.2.2.1 Cumulative Incidence Curves of Unprovoked Seizures using Kaplan-Meier Curves by Barthel Index Total Score – Full Analysis Set](#)

[Figure 15.2.2.2 Cumulative Incidence Curves of Unprovoked Seizures using Kaplan-Meier Curves by Barthel Index Total Score – Per-Protocol Set](#)

Cumulative incidence curves of USs using Kaplan-Meier curves displayed by time of randomisation and treatment group for each category of the BI total score.

[Listing 16.2.3.3 Barthel Index – Enrolled Set](#)

The BI items and total score data will be listed by treatment group.

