#### **2.1.2 Secondary Objectives**

The secondary objectives of this trial are:

1. To assess if ESL treatment (started within 120 hours after stroke occurrence and continued for 30 days) changes the incidence of USs – within the first 12 months after randomisation as compared to placebo
2. To assess if ESL treatment (started within 120 hours after stroke occurrence and continued for 30 days) changes the incidence of USs during the course of the trial – until 18 months after randomisation as compared to placebo
3. To assess the number of acute symptomatic seizures (Ass)

To assess the effect of ESL treatment over 18 months follow-up period on:

4. Time to first US after randomisation
5. Number of Uss
6. Functional outcome, assessed by Barthel Index original 10-item version (BI)
7. Functional outcome, assessed by National Institutes of Health Stroke Scale (NIHSS)
8. Post-stroke depression, assessed by Patient Health Questionnaire (PHQ-9)
9. Overall survival

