## **Endpoint value**

The endpoint value for an efficacy variable is defined as the last non-missing value collected after first intake of IMP before or at the respective endpoint (within the time window of interest i.e. 6 month-period, 12 month-period and 18 month-period).

The endpoint for a safety variable is defined as the last non-missing value collected after first intake of IMP that is no baseline value.

**Absolute change from baseline** will be calculated as

$$\text{Absolute Change from Baseline at Visit } X = \text{Value at Visit } X - \text{Baseline Value}$$

**Relative change from baseline (%)** will be calculated as

$$\text{Relative Change from Baseline at Visit } X = \frac{\text{Value at Visit } X - \text{Baseline Value}}{\text{Baseline Value}} \times 100$$

Note: Patients with a baseline value of '0' will be excluded from the calculation of relative change.

See section 5.4.1 for the definition of first and last IMP intakes.

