## **5.5.2 Analysis of Secondary Efficacy Variables**

The FAS and the PPS will be used for the analysis of secondary efficacy variables.

All data will be analysed as reported and missing data will not be imputed.

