Cumulative incidence of USs will be illustrated using Kaplan-Meier curves by the NIHSS baseline categories (<11, ≥11) and treatment group. Patients without an event or lost to follow-up will be censored at their last visit or termination date. Time to event will be calculated from time of examination since randomisation to first US.

The following statistical outputs will be presented:

[Table 15.2.7.1.1 Summary of NIHSS Total Score – Full Analysis Set](#)

[Table 15.2.7.1.2 Summary of NIHSS Total Score – Per-Protocol Set](#)

The default summary statistics for the NIHSS total score will be presented by treatment group by visit slots at Baseline, V2, V3, V5, V7, EOT, EDV (if applicable) and Endpoint.

[Table 15.2.7.2.1 Analysis of NIHSS Total Score Differences – Full Analysis Set](#)

[Table 15.2.7.2.2 Analysis of NIHSS Total Score Differences – Per-Protocol Set](#)

The Hodges-Lehmann estimate of location shift and the corresponding 95% CIs including the p-value will be presented by visit slots for V3, V5, V7 and Endpoint for ESL-Placebo.

Figure 15.2.3.1 Cumulative Incidence Curves of Unprovoked Seizures using Kaplan-Meier Curves by NIHSS Total Score – Full Analysis Set

Figure 15.2.3.2 Cumulative Incidence Curves of Unprovoked Seizures using Kaplan-Meier Curves by NIHSS Total Score – Per-Protocol Set

Cumulative incidence curves of USs using Kaplan-Meier curves displayed by time after randomisation and treatment group for each category of the NIHSS total score.

Listing 16.2.3.4 National Institutes of Health Stroke Scale (NIHSS) – Enrolled Set

The NIHSS items and total score data will be listed by treatment group.

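### The Barthel, NIHSS and PHQ-9 comparison tables omit the observed end-of-trial visit, so the only row that can reach 18 months is an Endpoint that is partly carried forward and has no stated window

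*SAP*

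**What the plan says.** The SAP's secondary objectives for BI, NIHSS and PHQ-9 share a lead-in that sets the horizon: "To assess the effect of ESL treatment over 18 months follow-up period on".

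Sections 5.5.2.5 to 5.5.2.7 each plan a descriptive table and a comparison table.

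- The descriptive BI table reports scores "at Baseline, V3, V5, V7, EOT, EDV (if applicable) and Endpoint". PHQ-9 has the same rows, and NIHSS adds V2. EOT and Endpoint are separate rows in all three.
- The BI comparison tables (15.2.6.2.x) "will be presented by visit slots for V3, V5, V7 and Endpoint for ESL-Placebo". The NIHSS and PHQ-9 tables (15.2.7.2.x and 15.2.8.3.x) use the same list: "95% CIs including the p-value will be presented by visit slots for V3, V5, V7 and Endpoint for ESL-Placebo".

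Section 4.8 says the Endpoint for an efficacy variable "is defined as the last non-missing value collected after first intake of IMP before or at the respective endpoint", and qualifies this as "within the time window of interest i.e. 6 month-period, 12 month-period and 18 month-period".

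On missing data, section 5.5.2 states: "All data will be analysed as reported and missing data will not be imputed". Section 4.10 says the same of everything other than the primary endpoint.

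**The concern.** The stated horizon is 18 months, and the visit that observes it is EOT. The last purely observed visit with a treatment comparison is V7, at target Day 365. Beyond that there is only Endpoint, which mixes EOT scores with scores from whenever other patients were last assessed. That could be as early as V3, or V2 for NIHSS.

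These scores are expected to move with time. Section 5.5.2.5 describes BI as a way to monitor improvement, and section 4.8 sets the NIHSS baseline at the worst post-stroke value. Change from baseline therefore depends on when a patient was last seen. If one arm loses patients earlier or in greater number, Endpoint can show a difference that does not exist at 18 months, or hide one that does. A patient who died contributes the last score recorded in life.

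The programmer also has to choose a window, because the tables list a single Endpoint and section 4.8 defines three.

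**Working it through.** **1. The lists side by side** (SAP 5.5.2.5, 5.5.2.6 and 5.5.2.7)

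| Scale | Collected after baseline | Descriptive rows after baseline | Comparison rows | Timing of the test in the methods text |
|---|---|---|---|---|
| BI | V3, V5, V7, EOT or EDV | V3, V5, V7, EOT, EDV, Endpoint | V3, V5, V7, Endpoint | every examination |
| NIHSS | V2, V3, V5, V7, EOT or EDV | V2, V3, V5, V7, EOT, EDV, Endpoint | V3, V5, V7, Endpoint | every examination |
| PHQ-9 | V3, V5, V7, EOT or EDV | V3, V5, V7, EOT, EDV, Endpoint | V3, V5, V7, Endpoint | not stated |

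EOT is in 3 of 3 descriptive lists and 0 of 3 comparison lists. Because EOT and Endpoint are separate descriptive rows, Endpoint is not another name for EOT. For BI and NIHSS the methods text and the table list disagree about EOT, and for NIHSS also about V2.

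**2. What Endpoint contains**

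Section 4.7 ends the 18-month period at Day 547 or the scheduled EOT. With that window, a completer's Endpoint is the observed EOT score. A patient without an EOT score contributes the last earlier one (EDV, V7, V5, V3, or V2 for NIHSS). With the 6- or 12-month window (to Day 182 or Day 365), no comparison would reach 18 months at all.

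**3. Size on the mean scale**

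The documents state no figure for these comparisons, so there is none to reproduce. They give no 18-month dropout rate and no expected recovery. Everything in this step is therefore an assumption except the form of the calculation.

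Let d be the share of an arm without an EOT score and R the mean change those patients would still have had between their last assessment and EOT. Then

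mean Endpoint = mean EOT − d × R.

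With no true difference at EOT, the spurious ESL − placebo difference is

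shift = −(d_ESL × R_ESL − d_placebo × R_placebo).

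With equal R this is −(d_ESL − d_placebo) × R. In absolute BI points:

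| Dropout gap | R = 10 | R = 20 |
|---|---|---|
| 0 | 0 | 0 |
| 5 percentage points | 0.05 × 10 = 0.5 | 0.05 × 20 = 1.0 |
| 15 percentage points | 0.15 × 10 = 1.5 | 0.15 × 20 = 3.0 |

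The only planned loss figure is the protocol's 5% missing in each arm at 6 months, excluding deaths. It is equal between arms, so with equal R it gives a shift of 0.

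For the number of values affected: if 5%, 15% or 30% of the planned 200 patients lacked an EOT score, 10, 30 or 60 Endpoint values would be carried forward. SAP 2.6 says recruitment stopped short of 200, so the actual counts would be lower.

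**4. Size on the planned test**

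The plan uses Wilcoxon and Hodges-Lehmann, not a difference in means. I simulated 100 patients per arm with no true EOT difference, normally distributed changes (assumed SD 25 or 30) rounded to 5-point steps, and 2,000 replicates per setting.

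- Loss of 30% vs 15% with R = 20: the median Hodges-Lehmann estimate moved by one 5-point step, and p < 0.05 occurred in about 10% to 12% of runs.
- Loss of 15% vs 10% (R = 10 or 20), or 30% vs 15% with R = 10: the median estimate was 0, and p < 0.05 occurred in about 5% to 8% of runs.

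**The case against.** The case on the other side has five parts.

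- **Endpoint is bounded.** A reader might infer that Endpoint is the last value ever recorded, or is carried forward for everyone. Section 4.8 limits it to a window, and a completer's 18-month Endpoint is the observed EOT score. Leavers should also have the scales taken at an early discontinuation visit, so many carried values would date from withdrawal. This stands: the carry-forward is partial.
- **The omission may be a drafting slip.** A reader might infer that the SAP deliberately plans no test at EOT. For BI and NIHSS the methods text covers every examination, including EOT, and the table shells are separate attachments. This stands as to intent. The two parts of the SAP still disagree, and the PHQ-9 text gives no timing that would settle it.
- **EOT is not hidden.** All three scales are summarised by arm at EOT. This stands: what is missing is the estimate, interval and p-value.
- **The bias is hypothetical.** The 3-point figure needs a large, unequal, early loss that nothing in the documents predicts. This stands, and 3 points is the top of an assumed range that begins at zero.
- **Observed EOT has its own selection.** It covers only patients still under follow-up, so it is also biased if loss or death differs by arm. This stands. It argues against replacing Endpoint with EOT, but not against showing both.

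The tests are labelled exploratory and section 4.1 makes no multiplicity adjustment. That limits the weight of the point but does not remove the inconsistency.

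**Conclusion.** The point holds as an inconsistency in the planned outputs. No purely observed 18-month treatment comparison is tabulated for BI, NIHSS or PHQ-9. The one row that can reach 18 months is last observation carried forward for patients without an EOT score, which conflicts with section 5.5.2, and its window is not stated. That the 18-month window is meant is the natural reading of the objective, not something the tables say.

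No bias follows if dropout and later change are equal between arms. Under the assumed gaps and recovery, the mean shift is about 0.5 to 3 BI points. On the planned rank test it is material only at the extreme end.

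A reader might go further and conclude that the 18-month results will be biased or that the trial's main conclusion is at risk. The documents support neither: they give no evidence of unequal loss, and the primary endpoint does not use these scales.

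**What to change.** - Add the observed EOT slot to Tables 15.2.6.2.x, 15.2.7.2.x and 15.2.8.3.x, and V2 to the NIHSS tables.
- State in 5.5.2.7 when the PHQ-9 test is run, as 5.5.2.5 and 5.5.2.6 already do.
- Keep Endpoint, state its window as 18 months, and label it as a last-observation analysis that supports the EOT row. Say that for patients who died it uses the last score before death.
- Amend 5.5.2 (and 4.10) so that the no-imputation statement names Endpoint as the exception.

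The cost is small. The BI and PHQ-9 tables go from 4 rows to 5 and the NIHSS tables from 4 to 6, with the same code. The downsides are one or two more unadjusted exploratory comparisons per table, and an EOT row with fewer patients that is restricted to those still in follow-up; a footnote should say so. Ranking death as the worst outcome is a further choice of estimand that the sponsor may consider, but this correction does not depend on it.
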